2.0 TRIAL DESIGN

2.1 Trial Design

This is a double-blinded, parallel, sham-controlled study in PwMS and with significant disability of the upper limb (UL). Participants are exposed to a 6-week run-in period with standard occupational therapy and then randomized to 6 weeks of tSCS or sham combined with ongoing occupational therapy. After completion of the double-blind period, sham-treatment participants will be offered an additional 6 weeks open-label extension (OLE) where they receive active tSCS combined with occupational therapy. Participants in the original active group will be followed with no additional stimulation or occupational therapy to assess the durability of effects. The duration of the run-in, active treatment and extended follow (6 weeks each) are defined based in the previous results from a similar therapy for SCI.

Specific procedures to be performed during the trial, as well as their prescribed times and associated visit windows, are outlined in the Trial Flow Chart - Section 6.0. Details of each procedure are provided in Section 7.0 – Trial Procedures.

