6.0 TRIAL FLOW CHART

Table 2 Trial flow chart

Visit Number	1	2	3-6	7
Visit Title	Screening	Randomization Baseline	Double blinded assessment	OLE

Scheduled Week/Day	Day 0	Day 42	Days 42-61-84	Day 126
Scheduling Window by Days:	±2	±3	±3	±5
Administrative Procedures				
Informed Consent – Subject	X			
Inclusion/Exclusion Criteria	X			
Subject Identification Card	X			
Medical History	X			
Prior Medication Review	X			
Randomization		X		
Monitor Trial Device Compliance		X		
Clinical Procedures/Assessments				
9HPT		X	X	X
ARAT		X	X	X
mAS		X	X	X
NeuroQOL		X	X	X
MFIS		X	X	X
GIC		X	X	X
Safety		X	X	X

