7.1.2.2.2 Measurements of Upper-Limb Function

The Nine-hole peg test (9HPT) has been validated as the assessment of the hand function for MS⁴⁶, with 15 to 20% defined as the minimal clinically important difference. In order to capture the upper-limb functioning we will include the Action Research Arm Test for motor function. The smallest real difference/minimal detectable change is defined as 5.7 points for the ARAT54 and 5.5 points for the Box and Blocks Test in stroke55. The Asworth scale will be used for assessing spasticity and the NeuroQOL Upper Extremity function as a PRO relevant for upper-limb dysfunction. In addition we will include a validated scale for fatigue in MS such as the MFIS and a global scale such as GIC for identifying additional effects of PROs.

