8.0 STATISTICAL ANALYSIS PLAN

8.1 Statistical Analysis Plan Summary

Linear mixed-effects models will be used to test the association between treatment arm and all primary and secondary endpoints. These models will include an outcome measure as the dependent variable, treatment assignment, time of measurement, and their interaction as independent variables and a random intercept for participant and site to account for the longitudinal and clustered nature of the data. If imbalances exist in baseline characteristics between treatment groups, sensitivity analyses will be conducted by including the covariate in the mixed-effects models as an independent variable to determine the impact it may have on the desired association. For the primary outcome, the interaction between treatment assignment and the 6 weeks follow-up will be assessed, with statistical significance indicating a difference in the change in 9-HPT is present between treatment groups at V5. All other time points and outcome measures will be treated as secondary. These analyses will be conducted following the intention to treat principle. Additional exploratory analyses will be conducted on the per protocol population defined as those who completed at least 70% of therapeutic sessions.

Table 4 Statistical analysis plan

Study Design Overview	Transcutaneous Electrical Spinal Stimulation (tSCS) for Improving Upper Limb Function in People with MS
Treatment Assignment	Active stimulation: tSCS Sham: stimulations using a non-active electric stimulation
Analysis Populations	Intention to treat Per Protocol
Primary Endpoint(s)	Differences in the nine-hole peg test (9-HPT) affected hand in the tSCS treated vs. sham groups by the end of treatment (V3 vs V5)
Key Secondary Endpoints	1. Percentage of responders: 20% difference on the 9HPTd (minimal clinically important difference (MCID)) from baseline to end of the study 2. Change in the 9HPT dominant and non-dominant hand from baseline to end of the study 3. Change in the Action Research Arm Test (ARAT) from baseline to end of the study 4. Change in the modified Ashworth Scale (mAS) for spasticity assessment from baseline to end of the study

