8.4.1. Efficacy Endpoints

Rationale for the key efficacy endpoints is given in Section 4.2.3.1 and an initial description of the efficacy measures is included in Section 7.1.2.2. In general, if a baseline value exists for a particular efficacy measure, then the change from baseline in that value will be evaluated.

Primary Endpoint

Differences in the nine-hole peg test (9-HPT) affected hand in the tSCS treated vs. sham groups by the end of treatment (V3 vs V5)

Secondary Endpoint

1. Percentage of responders: 20% difference on the 9HPTd (minimal clinically important difference (MCID)) from baseline to end of the study
2. Change in the 9HPT dominant and non-dominant hand from baseline to end of the study
3. Change in the Action Research Arm Test (ARAT) from baseline to end of the study
4. Change in the modified Ashworth Scale (mAS) for spasticity assessment from baseline to end of the study
5. Hand strength measured by Grip and Pinch force dynameters (Figure 10)
6. Change in the NeuroQOL Upper Extremity function from baseline to end of the study
7. Change in the Modified Fatigue Impact Scale (MFIS) from baseline to end of the study
8. Change in Global Impression of change (GIC) from baseline to end of the study

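### The GIC endpoint is written as a change from baseline in a scale that already rates change, with a Visit 2 rating scheduled as its baseline

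*Protocol*

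**What the plan says.** Section 8.4.1 of the protocol lists as its last secondary endpoint "Change in Global Impression of change (GIC) from baseline to end of the study". The same endpoint appears in the Trial Outline (Section 1.0), in Section 3.2 and in Table 4.

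The flow chart (Section 6.0) leaves the GIC row blank at Visit 1. It ticks the row at Visit 2, headed "Randomization Baseline" and set at Day 42, and again in the columns for Visits 3–6 and Visit 7.

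Two general statements then apply to the GIC without exception:

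- Section 8.4.1, in a sentence that opens with *In general*: "if a baseline value exists for a particular efficacy measure, then the change from baseline in that value will be evaluated".
- Section 8.1: "Linear mixed-effects models will be used to test the association between treatment arm and all primary and secondary endpoints", with "treatment assignment, time of measurement, and their interaction as independent variables".

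The scale itself is described only in Section 7.1.2.2.2, as "a global scale such as GIC for identifying additional effects of PROs". Section 2.1 states what comes before Visit 2: "Participants are exposed to a 6-week run-in period with standard occupational therapy".

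**The concern.** The ARAT, Ashworth, NeuroQOL and MFIS each measure a state at one moment, so a later value minus an earlier one is a change in that state. The GIC is different. By its own name it asks how much has changed, so the comparison with the past is already inside the score. Applying the same change-from-baseline template to it yields a difference between two change ratings that cover different periods.

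What is at stake is whether this secondary endpoint can be interpreted. Objective 2 (Section 3.1) expressly includes patient-reported outcomes, and the GIC is the one global scale among the efficacy measures. A reader of the results would expect the GIC to show how participants judged their change over the blinded period. The endpoint as written does not deliver that directly, and it may also be noisier than the direct rating.

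**Working it through.** The protocol gives no GIC figure to reproduce, so the main check sets its statements against each other. The arithmetic that follows is illustrative and rests on labelled assumptions.

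**1. Does the plan, read literally, subtract a baseline GIC?**

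- The endpoint sentence names a change from baseline.
- The flow chart supplies a baseline value at Visit 2.
- The general rule in Section 8.4.1 points to the change from that value.
- In the Section 8.1 model, with Visit 2 as the reference time, the treatment-by-time term at follow-up estimates

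  (mean follow-up − mean Visit 2) in tSCS − (mean follow-up − mean Visit 2) in sham.

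The model therefore performs the subtraction itself. No section says that the follow-up rating is analysed on its own.

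**2. What can the Visit 2 rating mean?** Visit 2 closes the six-week run-in. A rating there can be a constant (no change), an impression of the run-in, or, if taken after that day's session, an impression that includes one stimulation. Section 7.1.5.1.2 places vital signs and the neurological examination before the first stimulation but does not place the GIC. None of these possibilities is a starting level of the quantity rated at Day 84.

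An example shows the effect. Two participants give the same favourable rating at Day 84. One rated the run-in equally favourably and the other rated no change. The first scores zero on the endpoint and the second scores an improvement, although their Day 84 ratings are identical.

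**3. Is the between-arm contrast biased?** Suppose the GIC is rated before the first stimulation. Under randomisation the expected Visit 2 rating, m, is then the same in both arms. With expected Day 84 ratings A (tSCS) and S (sham),

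(A − m) − (S − m) = A − S.

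The subtraction leaves the expected contrast unchanged. The mean change in each arm, A − m or S − m, still has no clear meaning.

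**4. What happens to precision?** Let k be the ratio of the Visit 2 SD to the Day 84 SD, and r the correlation between the two ratings. Then

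Var(difference) / Var(Day 84) = 1 + k² − 2rk.

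With equal SDs (k = 1, assumed) this is 2(1 − r). The protocol gives neither k nor r. The last column assumes a standardised effect of 0.8 on the direct rating and 26 per arm, both borrowed from the 9HPT calculation in Section 8.9, with a two-sided t-test at 0.05.

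| r (assumed) | Variance ratio | SD ratio | Effect size | Power |
|---|---|---|---|---|
| Direct rating | 1 | 1 | 0.80 | 0.81 |
| 0 | 2.0 | 1.41 | 0.57 | 0.52 |
| 0.25 | 1.5 | 1.22 | 0.65 | 0.64 |
| 0.5 | 1.0 | 1.00 | 0.80 | 0.81 |
| 0.75 | 0.5 | 0.71 | 1.13 | 0.98 |

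At r = 0.3 the variance ratio is 2 × 0.7 = 1.4. If everyone rates no change at Visit 2, then k = 0, the ratio is 1 and nothing is lost. The effect on precision therefore runs from a doubled variance, through no effect, to a gain.

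**The case against.** The strongest reply is that the wording is loose drafting. Every item of this kind in the list follows one template, and the authors may simply have meant a GIC rated relative to baseline. The general rule is also qualified by *In general*, so it permits an exception. Both observations are fair, and it would be wrong to say that the rule compels the subtraction. They do not remove the defect: the endpoint sentence itself states the change, no exception is written, and the Visit 2 tick has no stated purpose if the follow-up rating is to be analysed directly.

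A reader might also infer that subtracting the Visit 2 rating removes or biases the treatment effect. The documents do not support that. A pre-stimulation rating has equal expectation in randomised arms, so the contrast survives. Nor do they establish that the rating is taken before stimulation, because the order within Visit 2 is not given. If it followed the first session, equal expectation would no longer be assured, but that too is not stated.

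The loss of precision is likewise not certain. It disappears at r = 0.5 under equal variances, reverses above that, and is absent if Visit 2 ratings are constant.

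Finally, the GIC version, its recall period and the choice of an ordinal or rank method can properly be left to the SAP. Their absence is not part of this point. The endpoint sentence, the schedule and the model are already fixed in the protocol.

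**Conclusion.** The point holds as a defect of definition in one secondary endpoint. Taken literally, the plan analyses a change in a change rating, using as baseline a value that is not the starting level of what is rated later. The certain consequence is that the within-arm mean changes lack a clear meaning; the only exception is a constant rating of no change at Visit 2.

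A possible further consequence is lost precision. The variance is at most doubled over non-negative correlations if variances are equal, and there is no loss at r = 0.5. The correlation and the equal variances are assumptions, and the power figures borrow an effect size that the protocol states for another outcome.

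The between-arm contrast is unbiased provided the GIC is rated before the first stimulation. The 9HPT primary analysis and the sample size are untouched. The text should be corrected, but the trial's main conclusion does not depend on it.

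**What to change.** Make two edits.

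1. **Flow chart (Section 6.0).** Remove the GIC tick at Visit 2, or label it a run-in rating that is not used as an efficacy baseline. Treat any other GIC taken on Day 42 in the same way, since the Visits 3–6 column also begins on that day.
2. **Endpoint (Sections 1.0, 3.2, Table 4 and 8.4.1).** Restate it as the GIC rating at the end of the double-blind period (Day 84), anchored to change since randomisation or the start of stimulation, and compared directly between arms without subtracting a Visit 2 score. Add a clause exempting the GIC from the change-from-baseline rule and from use of a Visit 2 record in the Section 8.1 model.

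Naming Day 84 also settles what the end of the study means for this endpoint. The flow chart runs to Day 126, by which time sham participants may have received active stimulation in the extension, so a Day 126 rating would not be a blinded tSCS-versus-sham comparison.

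The cost is one tick and one endpoint sentence, carried through the places where it is repeated. It should be done before GIC data are collected, because a reference period cannot be added to ratings already given.

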8.4.2 Safety Endpoints

Presence of serious adverse events (together with items of special attention)

An initial description of the safety measures is included in Sections 7.1.2.1, 7.1.2.2.10 and 7.1.3. Safety and tolerability will be assessed by statistical and clinical review of the following data collected throughout the study: adverse experiences (AEs), and treatment-emergent suicidality. The primary time for safety analyses is Visit 2; Safety endpoints are classified into 2 tiers (see Statistical Methods for Key Safety Analyses in Section 8.1 for Tier definitions).

Tier 1 Safety Endpoints include (the proportion of subjects with):

1. Any AE
2. Any Serious AE
3. Any treatment-Related AE
4. Any Serious and treatment-Related AE
5. Discontinuation due to AE

Tier 2 Safety Endpoints include:

1. Specific AEs, SOC AEs or PDLCs which have incidence in all 3 subjects.

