Measurements & Procedures	
 1. tSCS 2. Occupational Therapy 3. Clinical scales and PROs
Study Product / Intervention	tSCS is a non-invasive electric stimulation system that has shown good tolerability and signs of efficacy for improving UL disability
Controls	Sham (fictitious stimulation) will be used as control arm
Number of Participants & Rationale	
N=60 (30:30)
 
Rationale: accepting an alpha risk of 0.05 and a beta risk of 0.1 in a two-sided test, 10 subjects are necessary in each group to recognize as statistically significant a minimum difference of 10 units on the 9HPT scale between any pair of groups assuming that 2 groups exist. The common deviation is assumed to be 5.5. It has been anticipated a drop-out rate of 10%.

Study Duration:	
24 months
 
6 months recruitment, 9 months randomized phase, 6 months OLE, 3-month analysis and clinical scientific report

Timelines:	
 ● First Patient First Visit (FPFV): January 1st, 2025 ● Last Patient Last Visit (LPLV): December 30th 2026
Study Schedule:	
Patients in Spain are recruited from the three MS centers (Hospital del Mar, Hospital Clínic and Hospital Sant Pau) in Barcelona and treated in a single therapy center at Hospital del Mar located closely to all of them. Patients in the Netherlands are recruited at the Rijndam center, Erasmus Medical Center.
 
Run-in period (6 weeks with occupational therapy)
 
Double-Blinded period: 6 weeks for safety and efficacy assessments

	Open Label Extension (6 weeks) for safety and durability of efficacy
Study Center:	Hospital del Mar (HMar); Hospital Clinic of Barcelona (HCB); Hospital Sant Pau (HSP), all in Barcelona, Spain; Rijndam center, Erasmus Medical Center (EMC)
Statistical Analysis Plan	
The primary and secondary endpoints will be assessed using linear mixed-effects models (LME). These models will include the outcome measure as the dependent variable, and treatment group, time, and their interaction as independent variables, with random intercepts for participant and site to account for the longitudinal and clustered nature of the data.
 
Populations : 1) Intention to treat population; 2) Per protocol population: patients that completed 70% of the therapeutic sessions

A list of abbreviations used in this document can be found in Appendix 12.3.

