3.0 OBJECTIVE(S) & HYPOTHESIS(ES)

3.1 Co- Primary Objective(s) & Hypothesis(es)

Objectives:

- Objective 1. To assess the safety and tolerability of tSCS in PwMS.
- Objective 2. To assess the preliminary efficacy of tSCS on relevant clinical endpoints for PwMS, including patient-reported outcomes. This will be assessed by the differences in the

nine-hole peg test (9-HPT) affected hand in the tSCS treated vs. sham groups by the end of treatment (V3 vs V5)

Hypothesis:

We hypothesize that cervical tSCS combined with therapy will be tolerable and feasible in PwMS and enhance functional recovery of the upper extremity when compared to occupational therapy alone.

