7.1.5.1.2 Visit 2: Baseline

Patients will be randomized to either treatment or sham stimulation and assigned a code. Before starting stimulation, the researcher will conduct a vital signs and neurological examination. Then, the patient will be subjected to the first tSCS stimulations (a 30 min stimulations).

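### Section 8.4.2 makes Visit 2, the Day 42 randomisation and baseline visit, the primary time for safety analyses, so the primary time leaves out nearly all of the 6-week double-blind course

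*Protocol*

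**What the plan says.** Section 8.4.2 (Safety Endpoints) fixes the time: "The primary time for safety analyses is Visit 2". The same section lists the Tier 1 endpoints, the last of which is "Discontinuation due to AE".

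The flow chart in section 6.0 titles Visit 2 "Randomization Baseline" and schedules it at Day 42. Section 7.1.1.9 has the participant randomised at that visit. Section 7.1.5.1.2, headed as the baseline visit, describes pre-stimulation examinations and continues: "Then, the patient will be subjected to the first tSCS stimulations (a 30 min stimulations".

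Treatment lasts 6 weeks (section 5.2.2). The outline in section 1.0 describes the blinded phase as "Double-Blinded period: 6 weeks for safety and efficacy assessments". Section 3.1 places safety first among the co-primary objectives: "Objective 1. To assess the safety and tolerability of tSCS in PwMS".

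**The concern.** A primary time for safety should span the exposure whose safety is in question. Here it is the visit at which that exposure starts. Taken literally, the primary between-arm summary of the Tier 1 endpoints would describe the opening of treatment, and everything seen in the rest of the six weeks would be secondary.

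This matters because safety and tolerability is a co-primary objective of a pilot meant to inform later pivotal trials. Discontinuation due to an adverse event shows the problem most clearly. It accrues over repeated sessions, so a participant who stops in, say, the fourth week would not count at the primary time.

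**Working it through.** **1. What Visit 2 is.** Three places agree: the flow chart (randomisation and baseline, Day 42), section 7.1.1.9 (randomisation at Visit 2) and section 7.1.5.1.2 (baseline examinations, then stimulation starts).

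**2. How much of the course it covers.** Inputs from the flow chart: Visit 2 at Day 42, last double-blind assessment at Day 84, windows of ±3 days on each.

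- Nominal double-blind course: 84 − 42 = 42 days, which agrees with the 6 weeks in sections 1.0 and 5.2.2.
- Share taken by one visit day: 1/42 = 2.4%.
- With both windows at their limits, the course is (84 − 3) − (42 + 3) = 36 days to (84 + 3) − (42 − 3) = 48 days. The share is then 1/36 = 2.8% to 1/48 = 2.1%.

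The number of stimulations at the visit does not change this. Section 7.1.5.1.2 describes a 30-minute first stimulation, while section 7.1.4.1 speaks of three planned within visit 2. Either way it is one visit at the start.

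**3. Whether another numbering rescues the sentence.** The protocol numbers its visits in several ways:

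| Place | Use of visit numbers |
|---|---|
| Section 6.0 | Visit 2 baseline; Visits 3–6 double-blind; Visit 7 extension |
| Section 7.1.1.9 | Randomisation at Visit 2, but screen failure recorded at Visit 4 |
| Section 7.1.5.1.3 | Visits 3–5 are stimulation visits |
| Second section numbered 7.1.5.1.2 | Visits 13, 14 and 29 are the end of the double-blind period and the start and end of the extension |
| Sections 7.1.2.2, 7.1.4.1, 7.2.3.2 | Visit 2 treated as the stimulation period itself |

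No scheme makes Visit 2 the end of the double-blind period. The last row suggests text from a design in which all stimulation took place at one visit; that is an inference about origin, and the point does not depend on it.

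**4. Whether another passage sets a different primary time.** None does. Sections 3.4, 4.2.3.2, 8.4.2 and 8.6 describe safety data as gathered throughout the study, and the flow chart marks safety at Visit 2, Visits 3–6 and Visit 7. These govern collection and review, not which time is primary.

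**5. Where the primary window should close.** Section 2.1 says that after the double-blind period "sham-treatment participants will be offered an additional 6 weeks open-label extension (OLE) where they receive active tSCS combined with occupational therapy", whereas "Participants in the original active group will be followed with no additional stimulation or occupational therapy to assess the durability of effects". From then on the randomised labels no longer separate active from sham stimulation. Simply writing that the primary time is the whole study would therefore not work. By the flow chart that spans Day 0 to Day 126, of which only 42/126, one third, is the double-blind course; the rest is the run-in before randomisation and the extension phase.

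**6. The Tier 2 definition in the same section.** Section 8.4.2 defines Tier 2 specific events by an incidence in all three subjects, which has no referent in a trial of 60. Section 8.6 puts an event in Tier 1 if at least 4 participants in any group have it, and Table 5 puts it in Tier 2 if fewer than 4 do in every group, that is, 3 or fewer per group. The two sections give different definitions.

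**The case against.** The strongest reply is that little follows from the sentence. The term primary time is never defined, and the sentence just before it covers data from the whole study. Table 4 gives the key safety analysis as descriptive, and Table 5 as printed marks confidence intervals but no p-values for Tier 1. No alpha, stopping rule or go/no-go criterion depends on Visit 2. All of this stands, and it limits the weight of the point. It does not remove it: the protocol names a primary time, and an analysis plan that used another window would contradict the protocol.

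Three stronger readings are tempting and not supported:

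- A reader might infer that safety after Visit 2 goes unrecorded or unanalysed. The flow chart and sections 3.4, 8.4.2 and 8.6 say otherwise.
- A reader might infer that Visit 2 contains a single stimulation and nothing more. Section 7.1.5.1.2 suggests one, but section 7.1.4.1 has three.
- A reader might infer that discontinuation due to an adverse event cannot be observed at Visit 2. Section 7.1.4.1 provides for discontinuation during that visit, so the endpoint is truncated, not empty.

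It is also fair to say that the outline gives the open-label extension a safety purpose of its own. The fix must keep those data, though not inside the active-versus-sham comparison. Finally, borrowing the Table 5 rule for Tier 2 does not settle everything in section 8.6: its text promises p-values for Tier 1 and confidence intervals for Tier 2 that Table 5 does not mark, and it mentions a Tier 3 where section 8.4.2 has two tiers.

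**Conclusion.** The point holds as an error in a stated rule. Section 8.4.2 names a primary safety time that covers one visit day of a nominal 42-day double-blind course, about 2.4% (2.1% to 2.8% across the visit windows). That does not serve Objective 1 and truncates a Tier 1 endpoint in the same section.

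The percentage assumes that Visit 2 is a single day and that the flow chart's days are the operative schedule. The effect on event counts cannot be worked out, because the protocol gives no event rates. The data needed for a correct analysis will exist in any case. This should be fixed, but it does not threaten the conduct of the trial. The mismatch in the Tier 2 definition is a separate, smaller error in the same section.

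**What to change.** Replace the sentence in section 8.4.2 with: *The primary between-arm safety comparison covers all Tier 1 endpoints from each participant's first stimulation to their end-of-double-blind visit, before sham participants are offered active tSCS; open-label extension and follow-up safety data are summarised separately.* Anchoring the window to each participant's own visits, not to nominal Days 42 and 84, respects the ±3-day windows.

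Replace the Tier 2 wording in section 8.4.2 with the Table 5 rule (fewer than 4 participants in every treatment group).

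Reconcile the uses of visit 2 in sections 7.1.2.2, 7.1.4.1 and 7.2.3.2, and the visit numbers in section 7.1.1.9 and in the section on Visits 13, 14 and 29, with the flow chart and the description of Visit 2 in section 7.1.5.1.2. How many stimulations Visit 2 contains is for the sponsor to settle; the passages must agree.

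The cost is wording only. Safety is already recorded at Visit 2 and at every later visit, so no new visits, assessments or participants are needed.
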